**Visit 4 (virtual/telephone or in person):**

- Anthropomorphic measures (weight, % body fat, % muscle mass, % water, % bone) – at home or on scale in office
- Insulin pumps and CGMs will be downloaded to assess glycemic control. The diabetes treatment regimen will be adjusted as clinically indicated.
  - If participants are starting the very low carbohydrate diet, insulin doses will be reduced by 10-20%, as clinically indicated, to prevent hypoglycemia.
- Second diet will be assigned.

- If participants are starting the very low carbohydrate diet, meals can be picked up 2-3 times per week at the metabolic kitchen located at Yale New Haven Hospital by study participants or by research staff. Research staff will work with participants to deliver the meals if they are unable to pick them up.
- If we are unable to acquire meals from the metabolic kitchen, we will use a mail order meal service that provides information about macronutrient content of all meals provided that meet the standards of the dietary measures.
- Participants will be instructed to check daily fasting blood ketone levels.
- Participants will receive dietary instruction and review the dietary requirements of the study. Participants will be instructed to keep a dietary record (MyFitnessPal application, written, and/or with photos) for the duration of the dietary period.
- Participants will be instructed to call the pediatric diabetes emergency line (available 24/7) in any case of severe low blood sugar, elevated ketone levels, or symptoms of ketosis. Participants will also receive education on the treatment of hypoglycemia, we will ensure that all participants have glucagon at home.
- Participants will be contacted 3 times per week (2 scheduled, 1 unscheduled) for a 24-hour dietary recall. During these telephone follow up calls, food diary will be reviewed, ketone levels reviewed, and CGM data will be uploaded and reviewed.
- Prior to the HRU/CSRU/Masonicare admission, we will recommend a standard diet be given and no food be eaten after 12am (except for in cases of hypoglycemia). A snack will be recommended at 9pm the evening prior to the clamp. Participants will be advised to limit exercise in the 3 days prior to study to limit acute effects of recent exercise on insulin sensitivity.

**HRU/CSRU/Masonicare (Visits 3 & 5):**

- Participants will arrive the evening prior to the study or the morning of the study at 7am.
- Anthropomorphic measures (height, weight, BMI, vital signs)
- Urine pregnancy test (if participant is post-menarche)
- Insulin pumps and CGMs will be downloaded to assess glycemic control. The diabetes treatment regimen will be adjusted as clinically indicated.
- Questionnaires will be administered using Qualtrics, including:
  - Diabetes Treatment Satisfaction Questionnaire (DTSQ), which includes eight items, six of which form a scale (scored 0-36) in which higher scores indicate greater treatment satisfaction (Bradley, 1994).
  - Open-ended questions about the diet.
- Two indwelling catheters will be placed, one into an antecubital vein for infusion of test substances and a second catheter into a contralateral vein for blood sampling. Blood draws for measurements of glucose and glycerol enrichment are listed in tables 3, 4, 5, and 6.
- Baseline laboratory assessments will include:
  - Glucose (YSI)
  - Free fatty acid levels
  - Glucagon
  - Beta-hydroxybutyrate
  - IGF-1 (measure of growth hormone secretion)
  - Hemoglobin A1c (if none obtained in the past 30 days)
- Visit 6:
  - Participants will meet with study staff over the telephone or over HIPAA-compliant Zoom. Interviews will be conducted (see interview script) in a private, confidential place and recorded using Otter software (<https://otter.ai>) that involves live transcription. Participants and their parents will be asked open-ended questions about their experiences following a very low

carbohydrate diet. Participant and parent interviews will be conducted together, however participants will also be given the opportunity to share their thoughts without parents present at the end of the interview. Interviews will last about 20-30 minutes.

**Figure 2.** Schedule of HRU/CSRU/Masonicare measurements.

Baseline glucose and glycerol turnover	Hepatic sensitivity to insulin (low dose insulin)	Peripheral sensitivity to insulin (high dose insulin)	Hypoglycemia
150-minute equilibration	Euglycemic Low Dose (90 minutes)	Euglycemic High Dose (120 minutes)	Hyperinsulinemic Hypoglycemic Clamp (60 minutes)

- **Equilibration Period:** The study will begin with a ~150 minute equilibration period with a stable isotope infusion during which we will aim to keep glucose levels stable. Non-radioactive, Stable Isotope Tracer Infusions will be employed to assess rates of glucose and glycerol metabolism at the end of the ~150-minute baseline equilibration period. From -150 to 0 min, 4.5 mg/kg of 6,6-H2-glucose (99% enriched; Cambridge Isotope Laboratories, Andover MA) will be followed by a continuous infusion at 0.06 mg/kg/min. H5- glycerol will be infused at 1.6  $\mu$ mol/kg followed by a constant infusion of 0.11  $\mu$ mol/kg/min to assess glycerol turnover. During the basal turnover period, a variable rate insulin infusion may be utilized to maintain plasma glucose between ~90-110 mg/dL. As results from prior participants become available, infusions of the isotopes may be adjusted in subsequent participants to ensure enrichment is not too low for measurement.
- **Oral Non-radioactive, Stable Isotope Tracer:** 3 ml/kg body water of deuterated water will be given orally in 3 divided doses, (1 ml/kg body water in the evening, 1 ml/kg body water overnight, and 1 ml/kg body water early morning). The total D2O given (3 ml per kg body water) is designed to raise body deuterium levels to 0.3% and is administered as described above to maintain steady state until the end of the study. An additional 4.5ml mixed in 1000 ml tap water will be available to participants to drink for thirst, however this is not required.
- **Low Dose Insulin Infusion Period to Assess Hepatic Sensitivity to Insulin:** After obtaining baseline samples, the low dose insulin (8 mU/M surface area/min) infusion will be added to the basal insulin requirement for 90 minutes along with a variable 20% dextrose infusion with a goal of maintaining plasma glucose at 90-95 mg/dL. Plasma glucose levels will be measured every 5 minutes at the bedside throughout the clamp procedure.
- **High Dose Insulin Infusion Period to Assess Peripheral Sensitivity to Insulin:** The high dose insulin infusion of 80 mU/M surface area/min will also continue for 120 minutes accompanied by a variable 20% dextrose infusion.(14) Plasma glucose will be monitored every 5 minutes during both insulin infusion periods by the YSI 2300 glucose analyzer to adjust dextrose infusion rates to maintain plasma glucose 90-95 mg/dL.
- **Measures of Oxidation:** Indirect calorimetry will be utilized at the end of the baseline equilibration period, low dose, and high dose insulin euglycemic insulin infusions to evaluate rates of glucose and fat oxidation.
- **Hyperinsulinemic hypoglycemia period to assess counterregulatory hormone responses:** At the end of the hyperinsulinemic euglycemic portion of the clamp, the insulin infusion will be reduced to 40 mU/M surface area/min and exogenous glucose infusion will be reduced to allow the plasma glucose to fall to ~55 mg/dL where it will be clamped for an additional 60 minutes. After this time, the insulin

infusion will be stopped and euglycemia restored by increasing the intravenous glucose infusion at the end of the study. Plasma glucose levels will be measured every 5 minutes at the bedside throughout the clamp procedure. Once euglycemia is restored, participants will be given a meal and given instructions for the next portion of the study prior to discharge home. The Edinburgh hypoglycemia questionnaire will be conducted by asking the participants questions after 20-25 minutes of hypoglycemia.

- Metabolite collection: Samples for measurements of glucose and glycerol enrichment as well as hormones and substrates will be obtained every 5-10 minutes during the baseline equilibration phase as well as during the final 30 minutes of low dose, high dose, and hypoglycemic phases. Blood samples collected as a part of this research will be stored by the YCCI core lab services.
- During the 2-step hyperinsulinemic euglycemic clamp, laboratory blood tests will include:
  - Glucose (YSI)
  - Insulin and free fatty acid levels
  - Glucagon levels
  - Stable isotope measurements
- During the euglycemia (after 0, 30, 45, 60 minutes of euglycemia) and hypoglycemia clamp (after 15, 30, 45, and 60 minutes of hypoglycemia), laboratory blood tests will include:
  - Glucose (YSI)
  - Epinephrine
  - Norepinephrine
  - Glucagon
  - Cortisol
  - Beta hydroxybutyrate
- During the hypoglycemia portion of the clamp, participants will be blinded to their glucose levels in order to collect information about hypoglycemia symptoms.

Dietary Records: Dietary records will be input into the ASA24 Dietary Assessment Tool (<https://asa24.nci.nih.gov>). The ASA24 application will calculate the daily macronutrient content ingested by each participant throughout the study period.

Insulin Pump/CGM records: Insulin pump and CGM data will be uploaded (Tidepool, Dexcom, Medtronic, Omnipod or Tandem site, depending on the insulin pump being used) and reviewed virtually, as is commonly done in clinical practice. Patients are trained on how to upload their pump and CGM data to the Tidepool (HIPAA compliant) website and videos are available online explaining how to upload these devices (<https://medicine.yale.edu/pediatrics/endocrinology/cdp/media-player/5619/>).

Interview Records: Interviews will be conducted by study staff over HIPAA compliant zoom or by telephone and recorded using Otter software. All interviews will be audio-recorded and transcribed verbatim and any identifying information will be removed from the transcript. Interview scripts will be used as a guide and evolve as the study progresses. Transcriptions will be reviewed for accuracy and coded using NVivo.

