## 5 Study Design

**5.1 General Design Description:** Currently, there are no specific dietary recommendations for adolescents with T1D. To fill this gap in knowledge, we will study a very low carbohydrate diet that limits carbohydrate intake to 15% of total daily calories. We hypothesize that, compared to a standard carbohydrate diet, adolescents with T1D on a very low carbohydrate diet will spend more time in the target glucose range, will have a more robust response to hypoglycemia, and will lessen hypoglycemia awareness. To test these, we will conduct a randomized crossover study to compare the metabolic and neurological responses to hypoglycemia in adolescents after following each isocaloric diet.

**5.1.1 Study Date Range and Duration:** 4 years

**5.1.2 Number of Study Sites:** The enrollment visit will take place at the Pediatric Diabetes Research Center at [name]. The clamp procedures will take place at the CSRU, HRU, and Masonicare.

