### 6.4.2 Sample Size Considerations

For all aims, we base our sample size on the unadjusted comparison of paired means, which is a conservative approach. Therefore, given that our statistical analyses will be based on adjusted models and models that specifically take into account within-person correlation in outcomes of interest, we should be sufficiently powered to answer our research questions.

Aim 1: The goal time in range in adolescents with T1D 60% +/- 10% of their time in the target range of 70-180 mg/dL but based on our preliminary work in this population we expect that the mean percent of time in range is around 50-55%. With 16 eligible subjects, we will have 80% power at the two-sided alpha of 0.05 to detect a minimum increase in the expected mean by 7.5% (from 50-55% on standard carbohydrate diet to 57.5-62.5% on low carbohydrate diet - an increase of 1.5 hours per day - an effect size of  $7.5\% \div 10\% = 0.75$ ), using a paired-sample t-test. If we assume 20% attrition, we will need 20 individuals for the study.

Aim 2: Using data from a previously published study, where changes in glucagon levels during 2-step euglycemic-hypoglycemic clamp in youth with T1D were assessed over a period of 1 year(15), we anticipate that with 16 subjects (n=20 with 20% attrition, see aim 1) we will have 80% power at the two-sided alpha of 0.05 to detect a between-diet change in mean glucagon levels of at least 9.5 pg/mL (standard deviation=12.5 pg/mL, effect size of  $9.5 \text{ pg/mL} / 12.5 \text{ pg/mL} = 0.75$ ), using a paired t-test. We will also report the incremental rise and area under the curve (AUC) as well as mean and peak glucagon levels.

Aim 3: Using estimates of variability (standard deviations [sd]=5 during euglycemia and sd=10 during hypoglycemia) from a previous study, with 16 subjects (20 subjects with 20% attrition) we will have 80% power at the two-sided alpha of 0.05 to detect an effect size in the range of 0.75-1.0, using a paired t-test, meaning that when on low carbohydrate diet, subject

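### A participant's two clamps need not share a research unit or assay run, and the fall to ~55 mg/dL is neither timed from a defined zero nor compared between diets

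*Combined protocol and SAP*

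**What the plan says.** Section 6.3.5 (Visits 3 & 5) lowers the insulin rate after the high-dose step, and the glucose infusion is "reduced to allow the plasma glucose to fall to ~55 mg/dL where it will be clamped for an additional 60 minutes". No duration or rate is given for the fall. Figure 2 goes straight from the 120-minute high-dose step to "Hyperinsulinemic Hypoglycemic Clamp (60 minutes", with no slot for it. Hormones are drawn "after 15, 30, 45, and 60 minutes of hypoglycemia" and the Edinburgh questionnaire is asked "after 20-25 minutes of hypoglycemia". Neither timing says whether the clock starts when the infusions change, when glucose crosses some threshold, or when it reaches ~55 mg/dL.

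On location, section 5.1.2 says "The clamp procedures will take place at the CSRU, HRU, and Masonicare". Section 6.1.2 names all three units for each clamp visit, and no rule keeps a participant in one of them.

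On assays, section 6.3.5 says "Blood samples collected as a part of this research will be stored by the YCCI core lab services", and section 7.9 repeats this. Neither mentions runs or batches. The equilibration paragraph adds: "As results from prior participants become available, infusions of the isotopes may be adjusted in subsequent participants".

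Section 6.4.2 plans Aim 2 for 80% power with 16 evaluable participants to "detect a between-diet change in mean glucagon levels of at least 9.5 pg/mL", with an SD of 12.5 pg/mL. The models in sections 6.5.1 and 6.5.2 list no unit, assay-run or period term.

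Much else is held the same at both clamps: insulin rates, glucose targets, 5-minute glucose checks, nominal sampling times, and blinding of the participant to glucose during hypoglycemia. Section 6.3.5 also asks for constant CGM high alerts and consistent activity across the two diet periods.

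**The concern.** The between-diet comparisons in Aims 2 and 3 rest on one within-person difference between two clamps. Whatever differs between those visits for reasons other than diet goes into that difference. An error shared by all samples of one clamp is not reduced by averaging the four time points.

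The three open features act differently.

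- **Unit and assay run.** Diet order is randomized in blocks (6.1.3), so differences unrelated to diet mainly add noise. The cost is precision.
- **Fall time.** Randomizing the order does not remove a difference that diet itself causes. Section 4.1 expects lower glycogen stores on the very low carbohydrate diet, and the Synopsis expects the clamp to show diet-related changes in hepatic and peripheral insulin sensitivity. Either could alter how fast glucose falls. Participants could then reach the same nominal sampling time having spent different lengths of time at low glucose on the two diets.

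The glucagon outcome of Aim 2 and the between-diet hypoglycemia symptom score of Aim 3 are the results exposed to both.

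**Working it through.** **1. The plan's own figure.** Inputs from section 6.4.2: n = 16 evaluable, difference 9.5 pg/mL, SD 12.5 pg/mL, two-sided alpha 0.05, paired t-test. Power comes from the noncentral t distribution with 15 degrees of freedom and noncentrality d × √16 = 4d.

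- The plan's rounded d = 0.75 gives 80.1%.
- The unrounded d = 9.5/12.5 = 0.76 gives 81.1%.
- Enrollment with 20% attrition is 16/0.8 = 20.

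The stated 80% and N = 20 reproduce.

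**2. Unit or run error, if 12.5 excludes it.** Let e be an independent error SD shared by all samples of one clamp. Then SD of differences = √(12.5² + 2e²). The values of e are assumptions, since the documents give none.

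| e (pg/mL) | SD of differences | Power at n = 16 | Evaluable n for 80% | Enrolled (n/0.8) |
|---|---|---|---|---|
| 0 | 12.50 | 81.1% | 16 | 20 |
| 1.25 | √159.4 = 12.62 | 80.3% | 16 | 20 |
| 2.5 | √168.75 = 12.99 | 78.1% | 17 | 22 |
| 3.75 | √184.4 = 13.58 | 74.4% | 19 | 24 |
| 5 | √206.25 = 14.36 | 69.6% | 20 | 25 |

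**3. Unit or run error, if 12.5 already includes it.** Section 6.4.2 takes the SD from a study of glucagon during clamps in youth over one year, so it may contain visit and assay variance. Removing an assumed 5, 10, 20 or 30% of the variance gives SD = 12.5 × √(1 − share) = 12.18, 11.86, 11.18 or 10.46. Power becomes 83.0, 84.9, 88.8 or 92.4%.

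**4. Fall time, with time zero read as reaching ~55 mg/dL.** The documents give no fall rates, so assume 1 and 2 mg/dL/min. From 70 to 55 takes 15/1 = 15 min or 15/2 = 7.5 min. Add 22.5 min, the midpoint of the 20-25 minute window. The Edinburgh score then falls 37.5 or 30 min after glucose crosses 70.

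**5. Fall time, with time zero read as the change of infusions.** From 90-95 to 55 is 35-40 mg/dL, which takes 35-40 min at 1 mg/dL/min and 17.5-20 min at 2 mg/dL/min. The score at 20-25 min would then precede the plateau at the slower rate and follow it at the faster one. The choice of zero therefore changes what is measured.

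**6. What a diet-linked offset would do.** With no true diet effect on glucagon and the SD kept at 12.5, an assumed offset of 1.25, 2.5, 3.75 or 5 pg/mL gives a false-positive rate of 6.6, 11.6, 20.3 or 32.2% instead of 5%. The documents give no way to convert minutes of fall time into pg/mL, so this shows sensitivity only.

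**7. Which comparisons are exposed.**

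| Comparison | Unit | Assay run | Fall time |
|---|---|---|---|
| Between-diet hormones and substrates in hypoglycemia | yes | yes | yes |
| Between-diet fasting and euglycemic measures | yes | yes | no, taken before the fall |
| Between-diet hypoglycemia symptom score | yes | no assay | yes |
| Euglycemia versus hypoglycemia score in one clamp | no between-visit component | no assay | no between-visit component |

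**The case against.** The strongest reply is that silence is not evidence of a problem. One core lab stores all samples, which is compatible with batching. One analyzer model is named for bedside glucose, and infusion rates, targets and sampling times are fixed. Staff control the fall through the glucose infusion with readings every 5 minutes. They may already use one unit and paired runs. This stands: the text shows that the differences can enter, not that they do.

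A reader might infer from the isotope sentence that hormone results are read out during the trial in split runs. It does not show that. It concerns isotope enrichment only, and results from earlier participants informing later ones fit equally well with both visits of a participant being run together.

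A reader might also infer that every within-person comparison in Aims 2 and 3 is affected. The last table in the working shows otherwise.

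The error sizes and fall rates have no source in the documents, and an error of 1.25 pg/mL costs under one point of power. A loss of power added on top of 12.5 may count the same variance twice. That also stands, which is why both directions are shown.

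Finally, if diet changes the fall through glycogen, the change may be part of the diet effect, and calling it bias is open to dispute. This is a good reason not to adjust for fall time in the main analysis. It is not a reason to leave it unreported, because the reader of a glucagon difference needs to know whether the stimulus was equal.

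Tables 3-5, cited in section 6.3.5 for the enrichment draws, are not visible in the text reviewed, so a sampling detail there cannot be excluded.

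**Conclusion.** The concern holds as a gap in standardization. No visible text requires the same unit or assay run for a participant's two clamps, defines time zero for hypoglycemia, or checks whether the fall takes equally long on each diet. Avoidable variation can enter the between-diet hormone and substrate comparisons through unit and run, and the between-diet symptom comparison through unit alone. Unequal fall time could make the stimulus before sampling differ by diet.

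The size is unknown. If 12.5 pg/mL excludes such error, an assumed 1.25 to 5 pg/mL per clamp takes Aim 2 power from 81% to between 80% and 70%. If 12.5 includes it, the 80% target is still met and there is power to gain. The documents do not support a claim that the trial is underpowered for this reason, or that the diet contrast is in fact biased. The case for change is that the safeguards are cheap and protect the main results of Aims 2 and 3.

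**What to change.** In section 6.3.5:

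- State that a participant's Visit 3 and Visit 5 samples are assayed in the same run.
- State that both clamps of a participant use the same unit where possible, and record the unit.
- Define the time zero from which the 15-60 minute samples and the Edinburgh score are counted.
- Reconcile the food instructions before the two clamps. The text under Visit 2 stops food at 9pm. The text under Visit 4 stops it at 12am and recommends a 9pm snack. This is a written difference between the two visits.

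In section 6.5.2, derive for each clamp, from the 5-minute YSI readings, the time from 70 to 55 mg/dL and the mean glucose over the 60-minute hold. Report both by diet with paired 95% confidence intervals. Label any analysis that adjusts for them as exploratory, because they arise after randomization and may be part of the diet effect.

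The cost is protocol wording and a short analysis addition, with no new samples. Scheduling becomes less flexible. Visit 3 assays wait about 3-5 weeks for Visit 5 (1-3 weeks of washout plus 2 weeks of diet).

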### 5.2 Outcome Variables

#### 5.2.1 Primary Outcome Variables

**Aim 1:** The primary efficacy outcome will be the time spent in the target range of 70-180 mg/dL during the second week on each diet. Secondary safety outcomes will include the time spent in the hypoglycemic (less than 54 mg/dL, less than 70 mg/dL) and hyperglycemic (greater than 180 mg/dL, greater than 250 mg/dL) ranges. We will also measure the average sensor glucose values, standard deviation, and coefficient of variation during the second week on each diet period. We will compare average and range of fasting beta-hydroxybutyrate levels during each diet period. Number of episodes of diabetic ketoacidosis and severe hypoglycemic events during each period (baseline, diet periods, and washout period) will also be reported.

**Aim 2:** The primary safety outcome will be the mean levels of glucagon produced in response to hypoglycemia after each diet will be measured using a 2-step hyperinsulinemic euglycemic-hypoglycemic clamp. These will be measured after 15, 30, 45, and 60 minutes of euglycemia and hypoglycemia. Secondary safety outcomes will include mean levels of other counterregulatory hormones (cortisol, epinephrine, norepinephrine), and beta-hydroxybutyrate that are produced in response to hypoglycemia during the clamp will be compared after each 2-week diet period. Fasting levels of glucagon, free fatty acids, beta-hydroxybutyrate and IGF-1 (measure of growth hormone secretion), prior to the clamp will be compared after each diet period. Secondary outcome measures will include hepatic glucose production and adipose tissue lipolysis, which will be measured using stable isotope infusions during the euglycemic and hypoglycemic portions of the clamp. We will compare differences in hepatic glucose production during each clamp between a standard and very low carbohydrate diet. Additionally, deuterated water will be utilized to differentially evaluate the contribution of gluconeogenesis and glycogenolysis to endogenous glucose production.

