#### **6.1.8 Restrictions- N/A**

### **6.2 Assessments**

#### **6.2.1 Efficacy**

Aim 1	
Primary Efficacy Outcome	Percent time spent in the target range of 70-180 mg/dL during 2 weeks on each diet, as measured by CGM.
Secondary Safety Outcomes	We will measure the percent time spent in the hypoglycemic (<54 mg/dL, <70 mg/dL) and hyperglycemic (>180 mg/dL, >250 mg/dL) ranges. We will also measure the average sensor glucose values, standard deviation, and coefficient of variation during each 2-week diet period. We will compare the average fasting $\beta$ -hydroxybutyrate levels during each diet period. Number of episodes of diabetic ketoacidosis and severe hypoglycemic events during each period (baseline, diet periods, and washout period) will also be reported.
Aim 2	
Primary Safety Outcomes	Mean levels of glucagon produced in response to hypoglycemia after each diet will be measured using a 2-step hyperinsulinemic euglycemic-hypoglycemic clamp. These will be measured every 15-30 minutes of during the first step of the euglycemic clamp and every 15 minutes during the hypoglycemic clamp.
Secondary Safety Outcomes	Measure mean levels of other counterregulatory hormones (cortisol, epinephrine, norepinephrine) and $\beta$ -hydroxybutyrate that are produced in response to hypoglycemia during the clamp will be compared after each diet period. Fasting levels of glucagon, free fatty acids, $\beta$ -hydroxybutyrate and IGF-1 (measure of growth hormone secretion) prior to the clamp will be compared after each diet period.
Secondary Efficacy Outcomes	Hepatic glucose production and adipose tissue lipolysis will be measured using stable isotope infusions during the euglycemic and hypoglycemic portions of the clamp. We will compare differences in hepatic glucose production during each clamp between a standard and very low carbohydrate diet.

Aim 3	
Primary Safety Outcome	We will measure hypoglycemia awareness symptoms after 20-30 minutes of euglycemia and hypoglycemia during each clamp using a validated Edinburgh Hypoglycemia Symptom questionnaire. Scores during euglycemia will be compared to scores during hypoglycemia for each clamp. Scores during hypoglycemia after each diet period will also be compared.

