### 6.5.2 Secondary Objectives Analyses

- **Statistical Analysis Aim 2:** Appropriate mathematical transformations (e.g., natural log or square root) will be applied to each outcome of interest, as necessary, to normalize the distribution. A paired t-test will be used in the unadjusted comparison of the primary outcome, mean levels of glucagon, during each diet period. LME will be used to model the trajectories of change in mean levels of glucagon over time (baseline, 15, 30, 45, 60 minutes) during each diet period and compared between diets. We will use the Likelihood Ratio Test (LRT, a mixture of two chi-square distributions with restricted maximum likelihood – RML - estimation) to select between an LME model with just a random intercept or an LME with a random intercept and slope. The mean response will be modeled using parametric (linear and polynomial effects of time) and semi-parametric (piece-wise linear or quadratic splines) effects of time, adjusting for participants' age, BMI, and duration of diabetes. The best model will be chosen based on its fit to the data (LRT for nested models and Akaike Information Criterion, AIC, for not-nested models).

Effect sizes will be reported as the between-diet differences with bootstrapped 95% CIs. Secondary outcomes of interest will also be modeled similarly.

- **Statistical Analysis Aim 3:** Using the validated Edinburgh Hypoglycemia Symptom questionnaire, participants will be asked to verbally rate their hypoglycemia symptoms on a 7-point Likert scale (lower scores indicate fewer symptoms) during the euglycemia and hypoglycemia portions of the clamp. In the unadjusted analyses, differences between euglycemic and hypoglycemic total scores on each diet will be compared using a paired t-test. Adjusted analyses will be based on LME, similar to the analyses described in Aims 1 and 2. In the secondary analysis, we will model mean hypoglycemia awareness score by domain (e.g., autonomic, neuroglycopenic, and malaise).

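### The euglycemic reference for the Aim 2 hormone responses is undefined, and the listed samples most naturally fall 150 to 210 minutes before glucose is lowered

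*Combined protocol and SAP*

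**What the plan says.** Figure 2 and the text of 6.3.5 (HRU/CSRU/Masonicare, Visits 3 & 5) set out the clamp: about 150 minutes of equilibration, 90 minutes of low-dose insulin, then "Euglycemic High Dose (120 minutes"), then 60 minutes of hypoglycemia. The insulin rate is 8 mU/m²/min on top of the basal requirement in the low-dose step, 80 in the high-dose step and 40 during hypoglycemia.

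The timing of the hormone samples is described in four ways:

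- **6.3.5, named panel** (epinephrine, norepinephrine, glucagon, cortisol, beta-hydroxybutyrate): "During the euglycemia (after 0, 30, 45, 60 minutes of euglycemia) and hypoglycemia clamp (after 15, 30, 45, and 60 minutes of hypoglycemia").
- **5.2.1, and the Synopsis in the same terms**, for glucagon: "These will be measured after 15, 30, 45, and 60 minutes of euglycemia and hypoglycemia".
- **6.2.1, outcome table**, for glucagon: "every 15-30 minutes of during the first step of the euglycemic clamp and every 15 minutes during the hypoglycemic clamp".
- **6.3.5, metabolite collection**: "Samples for measurements of glucose and glycerol enrichment as well as hormones and substrates will be obtained every 5-10 minutes" in equilibration, "as well as during the final 30 minutes of low dose, high dose, and hypoglycemic phases". The hormones are not named there. Glucagon is also listed among the tests for the whole 2-step euglycemic clamp.

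On analysis, 6.4.2 says: "We will also report the incremental rise and area under the curve (AUC) as well as mean and peak glucagon levels". Section 6.5.2 models the "trajectories of change in mean levels of glucagon over time (baseline, 15, 30, 45, 60 minutes") and treats the secondary hormones in the same way. The primary Aim 2 comparison is a paired t-test of mean glucagon between diets.

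**The concern.** A rise during hypoglycemia needs a starting value, and the plan does not name one. The model times of 15 to 60 minutes match the hypoglycemia draws, but that series has no draw at minute 0. Baseline must therefore be borrowed from one of four places: the pre-insulin draw, the 0-minute euglycemic draw, a later draw in the early euglycemic series, or a late high-dose draw. These differ in insulin level and in time before hypoglycemia.

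If an early one is used, whatever happens to glucagon or catecholamines as insulin changes and hours pass is counted as response to hypoglycemia. That affects the incremental rise, any baseline-corrected AUC and the modelled trajectory. For epinephrine, norepinephrine and cortisol the difficulty is greater. They are absent from the list of baseline laboratory tests, and the only panel that names them carries the early times. A draw that was not taken just before hypoglycemia cannot be recovered at analysis.

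**Working it through.** **1. The plan's own figure.** Section 6.4.2 claims 80% power for Aim 2 with 16 participants, a difference of 9.5 pg/mL and SD 12.5 pg/mL (two-sided alpha 0.05, paired t-test). The effect size is 9.5/12.5 = 0.76, printed as 0.75. With 15 degrees of freedom and noncentrality d × √16, power is 80.1% at d = 0.75 (noncentrality 3.00) and 81.1% at d = 0.76 (3.04). Enrolment is 16/(1 − 0.20) = 20. The figures reproduce, and none of them uses a euglycemic reference.

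**2. Timeline.** Take the start of low-dose insulin as 0. Low dose runs 0–90 and high dose 90–210, so glucose is lowered from minute 210. Lead = 210 − sample time.

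| Listed euglycemic sample | Lead if the clock starts with low dose | Lead if it starts with high dose |
|---|---|---|
| 0 min (6.3.5) | 210 min | 120 min |
| 15 min (5.2.1, Synopsis) | 195 min | 105 min |
| 30 min | 180 min | 90 min |
| 45 min | 165 min | 75 min |
| 60 min | 150 min | 60 min |

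On the first reading, the four samples in 6.3.5 have a mean lead of (210 + 180 + 165 + 150)/4 = 176 min, or 2.9 h. The 0-minute sample is at the start of low-dose insulin, not inside the step. The pre-insulin baseline samples lead by at least 210 min. The final-30-minute high-dose samples (180–210) lead by 30 to 0 min. The time for glucose to fall to about 55 mg/dL is not given and adds to every lead.

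**3. Which reading.** The reference to the first step in 6.2.1 supports the low-dose reading, but for glucagon only. No passage anchors the clock for the other hormones.

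**4. What an early reference does.** Let E be the early reference, L a value at the end of the high-dose step and H the value in hypoglycemia. Then

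H − E = (H − L) + (L − E).

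The second term is change before hypoglycemia begins. In the between-diet contrast,

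Δ(H − E) = Δ(H − L) + Δ(L − E),

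so the added bias is Δ(L − E). This is zero if the pre-hypoglycemia change is the same on both diets.

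**5. Could it differ by diet?** Low-dose insulin is added to the basal requirement (6.3.5), and the Aim 2 hypothesis in 4.1 expects lower insulin doses on the very low carbohydrate diet. Total insulin at an early reference, and the step from there to hypoglycemia, may therefore differ. The documents give no euglycemic glucagon values and no insulin levels by diet, so Δ(L − E) cannot be sized.

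**The case against.** The strongest reply has four parts.

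- **A late sample is already planned.** The metabolite collection in the last 30 minutes of the high-dose step includes hormones, and glucagon is on the list for the whole 2-step clamp. It is tempting to infer that nothing is measured shortly before hypoglycemia. The documents do not support that for glucagon, which is the only hormone with an explicitly planned incremental rise. For epinephrine, norepinephrine and cortisol it depends on what the unnamed hormones are.
- **The reference is undefined, not wrongly chosen.** A reader might infer that the rise will be taken from the low-dose samples. Nothing in 6.4.2 or 6.5.2 says so, and 6.4.2 does not say whether the AUC is baseline-corrected.
- **The primary comparison does not use the reference, and both diets share one clamp sequence.** A common insulin or time effect cancels in the paired difference. It would be too strong to say that the Aim 2 primary result is biased or its power reduced.
- **A late high-dose reference is imperfect.** It is taken at 80 mU/m²/min and the response at 40, and no euglycemic sample is planned at 40.

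All four stand, and they limit the point. They do not remove it. The sampling descriptions disagree, the starting value is unnamed, and for three hormones the only named euglycemic draws are the early ones.

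**Conclusion.** The point holds as a cheap improvement. The euglycemic sampling times are inconsistent, and the reference for the incremental rise and the model baseline is missing. On the most natural reading the listed draws end 150 minutes before glucose is lowered; on the reading most favorable to the plan they end 60 minutes before.

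If an early or pre-insulin sample becomes the reference, the within-clamp rise and the trajectory are not responses to hypoglycemia alone. The between-diet bias is only the diet-specific part of the earlier change: possible on the plan's own expectations, but of unknown size. The paired t-test of mean glucagon and its 80% power are not touched. This takes the mean over the hypoglycemic draws, as the outcome's wording implies.

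**What to change.** - Reconcile the Synopsis, 5.2.1, 6.2.1, 6.3.5 and 6.5.2. For each hormone, name the clamp step and the clock time of every draw.
- Move the euglycemic panel (glucagon, epinephrine, norepinephrine, cortisol, beta-hydroxybutyrate) to the final 30 minutes of the high-dose step, where blood is already drawn.
- Define the mean of those samples as time 0 for the incremental rise, any baseline-corrected AUC and the mixed model, and say whether the AUC is baseline-corrected.
- Keep the pre-insulin fasting sample as a separate fasting outcome, not as the model baseline.
- State that reference and response still differ in insulin rate (80 versus 40 mU/m²/min), so the within-clamp rise is not a pure hypoglycemia effect.

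The cost is protocol wording and a re-timed draw sheet. Draws should be moved, not added: Table 6 shows 208.7/43 = 4.85 mL/kg at 43 kg, against the pediatric ceiling of 5 mL/kg in 3.2.1. Sample size and infusions do not change. The early low-dose-step hormone values are lost; 5.2.1 lists early euglycemic glucagon within the outcome, so that text must change too.
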